Please see the section below on “Weaning of mechanical ventilation for both groups”

Intervention group (PHARLAP) mechanical ventilation

Initial commencement of mechanical ventilation in the PHARLAP group

Mode: After randomisation, patients should be commenced in either Assist-Control (A/C) or Synchronised Intermittent Mandatory Ventilation (SIMV) using Pressure Control mode. All patients should be commenced in controlled rate ventilation, even if this requires additional sedation and/or neuromuscular blocking drugs. The PEEP level should remain at the pre-randomisation level.

The combined open lung procedure in the PHARLAP group (see Figure 1)

The initial procedure of the PHARLAP mechanical ventilation strategy should be to perform the combined open lung procedure which consists of (1) a staircase recruitment manoeuvre (SRM), followed by (2) a PEEP titration manoeuvre, and followed by (3) a brief recruitment manoeuvre (see Figure 1). This initial combined open lung procedure should be performed within 4 hours of randomisation.

This will then be followed by PHARLAP strategy mechanical ventilation.

The combined open lung procedure should be performed after assessment by an intensivist or registrar and when haemodynamic resuscitation is complete and circulatory parameters are stable. If vasopressors or inotropes are being used, a small transient increase prior to the combined open lung procedure will minimise any hypotension.

The **contraindications to a recruitment manoeuvre** (both the staircase and the brief manoeuvre) are:

- Mean systemic blood pressure < 60 mmHg despite attempts to augment BP with vasopressors/fluids.
- An active air leak through an intercostal catheter.
- Any radiographical evidence of pneumatoceles, subpleural cysts, or pericardial or mediastinal emphysema.
- Subcutaneous emphysema not related to trauma, surgical procedures, or ICU procedures.
- A supraventricular tachycardia associated with a mean systemic blood pressure < 70 mmHg, or any ventricular tachycardia.

If a patient has a contraindication to the combined open lung procedure, all other aspects of PHARLAP mechanical ventilation should be continued until the contraindication has resolved (when the combined open lung procedure should then be performed).

The combined open lung procedure should be performed as follows:

(1) Staircase recruitment manoeuvre (SRM):

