The mechanical ventilator settings should be Pressure Control with an inspiratory pressure of 15 ± 3 cmH₂O depending on tidal volume achieved (pre-SRM tidal volume target 4-6 ml/kg PBW). The PEEP level should be left at the level it had been immediately prior to this procedure. The FiO₂ should be adjusted (usually by turning it down) until the SaO₂ is stable between 90-92%. This may take several (often 15-30 minutes). The high pressure alarm should be set to 65 cmH₂O and the low tidal volume and minute ventilation alarms reduced to < 25% of the current settings.

Once the FiO₂ is stable (ie. no change for 3 minutes), the PEEP should be increased from the pre-randomisation baseline to 20 cmH₂O. In a stepwise fashion, this should be increased after 2 minutes to 30 cmH₂O (for 2 minutes) and then 40 cmH₂O (for 2 minutes), unless there is occurrence of (a) haemodynamic instability (defined as heart rate < 40 or > 140 bpm, ventricular tachycardia, or systolic blood pressure (SBP) < 80 mmHg), (b) marked oxygen desaturation (SaO₂ < 85%) or (c) new air leak through an intercostal catheter. The tidal volume should not be adjusted at each PEEP level, unless the tidal volume is > 6 ml/kg PBW.

The patient may cough or become restless at high PEEP levels. This may be due to expansion of collapsed lung and does not require the SRM to be discontinued. Transient reductions in tidal volume and minute ventilation are to be expected as the PEEP levels are increased. Sometimes the patient will require additional sedation.

If haemodynamic instability, marked oxygen desaturation or a new air leak occurs during the SRM, the SRM should be abandoned (with no further increases in PEEP occurring above the level where this occurred). If the

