patient is considered to be inadequately haemodynamically resuscitated for their underlying condition, then it is preferable if vasopressor or fluid resuscitation should occur over the next 30-60 minutes, and then the combined open lung procedure be resumed. If the patient is considered to be adequately haemodynamically resuscitated, then fluid loading purely for the SRM should not be undertaken. The PEEP level one level below the PEEP level at which the SRM was abandoned should be determined as the **maximum tolerated PEEP** for this specific SRM and the PEEP titration manoeuvre should now occur (i.e. if marked desaturation occurs at 40 cmH₂O the maximum tolerated PEEP should then be determined as 30 cmH₂O). The maximum tolerated PEEP for the SRM will be determined daily and may be a different value on subsequent days.

If there is no occurrence of haemodynamic instability, marked oxygen desaturation or new air leak, the PEEP should be increased to the highest level of 40 cmH₂O. This should be determined as the maximum tolerated PEEP for this SRM.

(2) PEEP titration manoeuvre

After the final SRM step has been completed (or abandoned, as above), the PEEP should be immediately reduced to 25 cmH₂O. If, however, the SRM was abandoned at 20 cm H₂O, the PEEP titration should begin at 17.5 cm H₂O. The PEEP should be left at this first setting for 3 minutes, then decreased in steps by 2.5 cmH₂O for 3 minutes at each PEEP level to a minimum of 15 cmH₂O (i.e. from 25 to 22.5 to 20 to 17.5 to 15 cmH₂O) until the **de-recruitment PEEP** is reached. If the mechanical ventilator does not have 0.5 cmH₂O increments, round the PEEP up from 22.5 to 23 and 17.5 to 18 cmH₂O. The de-recruitment PEEP is defined as the PEEP level at which the SaO₂ first decreases by $\geq 2\%$. Once the de-recruitment PEEP has been reached, there should be no further reduction in PEEP, and the brief recruitment manoeuvre should now occur.

The PEEP should not be reduced below 15 cmH₂O if desaturation does not occur. In this situation, the PEEP should be left on 15 cmH₂O and no brief recruitment manoeuvre is required (i.e. the combined open lung procedure has been completed).

(3) Brief recruitment manoeuvre

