After this de-recruitment, a 2 minute brief recruitment manoeuvre should be performed (with the inspiratory pressure set at 15 ± 3 cmH₂O) using the PEEP level that was the maximum tolerated PEEP for the recently performed SRM. After this brief recruitment manoeuvre the PEEP should be returned to the level that is 2.5 cmH₂O above the de-recruitment PEEP. If there was no desaturation to determine the de-recruitment PEEP, the PEEP should be set at 15 cmH₂O and no brief recruitment manoeuvre is required. This final PEEP level should be considered the **daily optimal PEEP** (for the subsequent period - usually 24 hours) until a subsequent combined open lung procedure is performed.

Ventilation settings immediately after the combined open lung procedure

Plateau pressure, tidal volume and pH: Once the combined open lung procedure has been completed, the pressure control level should be reduced to achieve a total pressure (i.e. inspiratory pressure + PEEP) ≤ 30 cmH₂O (preferably 25-28 cmH₂O) and a tidal volume of 4-6 ml/kg PBW. The tidal volume should be titrated down from 6 ml/kg towards 4 ml/kg if possible. The set breath rate should also be reduced aiming for a lowish pH (in the range of 7.15-7.30). The actual pH in an individual patient will depend on other factors (including level of sedation and other metabolic issues) and should be a clinical decision at the time.

[figure not shown]
The mechanical ventilator alarms should be returned to their appropriate settings.

FiO₂ and PEEP: Immediately after the combined open lung procedure, the FiO₂ should be decreased until the SaO₂ is in the target range of 90-95%. One hour after the combined open lung procedure, the SaO₂ should be noted, and recorded on the bedside PHARLAP study ventilation sheet as the subsequent **daily precise SaO₂ target** for that day.

After this 1 hour time point, a SaO₂ $\leq 2\%$ below this daily precise SaO₂ target should prompt strong consideration of re-recruitment using a brief recruitment manoeuvre (with or without an increase in FiO₂).

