Brief recruitment manoeuvre: A brief recruitment manoeuvre should be performed independently (ie. without an SRM and individual PEEP titration) if an oxygen desaturation occurs ($\geq 2\%$ below the daily precise SaO₂ target). This may occur without a clear precipitating event or may occur as a result of (a) an intervention (eg. suction, cuff deflation, body position change, coughing episode, waking) or a mechanical ventilator disconnection. Disconnections include inadvertent extubations (followed by reintubation), and any inadvertent disconnections of the endotracheal tube or tracheostomy tube from the ventilator circuit however brief these may be. Disconnections for tracheostomy care and changes of in-line suction catheters should be followed by a brief recruitment manoeuvre. Disconnections occurring due to patient transfer for a procedure (eg. radiology department, operating theatre) or to move the patient to another ICU bedspace should be followed by a brief recruitment manoeuvre only after the patient has been reconnected to the ventilator back in the ICU. For example, a transfer to the radiology department may have several associated disconnections (from the ICU ventilator, from a transfer ventilator, from a ventilator in the radiology suite, from the transfer ventilator again). These should be considered together as one disconnection, and the brief recruitment manoeuvre performed only upon return to the ICU with reconnection to the ICU ventilator. If an episode of in-line suctioning is performed without a clear disconnection, a brief recruitment manoeuvre is not required.

Similarly to the combined open lung procedure, independently performed brief recruitment manoeuvres should not be performed if:

- (a) readiness for weaning criteria are met (see below),
- (b) lack of improvement in static lung compliance criteria are met (on day 3, see below),
- (c) there is a contraindication to a recruitment manoeuvre (see above), or
- (d) it is the 6th day after enrolment (ie. 5 days of combined open lung procedures have occurred).

If an oxygen desaturation ($\geq 2\%$ below the daily precise SaO₂ target) occurs with a clear precipitating event (i.e. intervention or ventilator disconnection), the brief recruitment manoeuvre should be performed as follows:

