- The PEEP should be increased to the maximum tolerated PEEP determined during the most recently performed SRM, left at that level for 2 minutes, and then immediately returned to the daily optimal PEEP determined by that same SRM.

If an oxygen desaturation ($\geq 2\%$ below the daily precise SaO₂ target) occurs with no clear precipitating event (ie. potentially a deterioration in lung function), the brief recruitment manoeuvre should be performed as follows:

- The PEEP should be increased to the maximum tolerated PEEP determined during the most recently performed SRM, left at that level for 2 minutes, and then immediately returned to 2.5 cmH₂O (rounded up by 0.5 if the ventilator does not use 0.5 cmH₂O settings) higher than the previous daily optimal PEEP set during that SRM.
- This new PEEP level should be considered the new daily optimal PEEP level for the subsequent part of that day until the next SRM is performed. The FiO₂ should then be decreased as required to maintain the SaO₂ aim.
- The PEEP should not be set higher than 25 cmH₂O at any time during the study (with the exception of the staircase recruitment manoeuvre).

Brief recruitment manoeuvres should not be repeated more frequently than 2 hourly and not more than a maximum of 4 manoeuvres per 24 hours.

Ventilation during patient transfers: Mechanical ventilation should continue to adhere to this PHARLAP group strategy during patient transfers (to diagnostic or therapeutic procedures outside the ICU) where possible. However if the patient receives mechanical ventilation using either a manual (hand-bagging) circuit or a transport ventilator that is not practically able to deliver the PHARLAP group mechanical ventilation settings, patients may be ventilated using alternative means whilst away from the ICU. Resumption of PHARLAP group mechanical ventilation (including performance of a brief recruitment manoeuvre if indicated)

should occur as soon as possible after the transfer. A brief recruitment manoeuvre will usually be required (see above on this page).

Specific measurements on Day 3 in the PHARLAP group

Patients in both groups should have 2 things measured on day 3:

1. Static respiratory compliance should be measured (see page 22 for technique).
2. Specimens of blood and BAL should be collected (see below) – **after** static respiratory compliance has been measured. The BAL should be collected using the same technique as was used at baseline.

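### The 25 cmH₂O cap on PEEP excepts only the staircase manoeuvre, yet independent brief recruitment manoeuvres are ordered at 40 or 30 cmH₂O

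*Combined protocol and SAP*

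**What the plan says.** The cap is the final bullet under Ongoing recruitment manoeuvres in the PHARLAP group, in the instructions for a brief manoeuvre after a desaturation with no clear cause: "The PEEP should not be set higher than 25 cmH₂O at any time during the study (with the exception of the staircase recruitment manoeuvre". Only the staircase recruitment manoeuvre (SRM) is excepted.

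The same instructions give two versions of the independent brief manoeuvre, for desaturation with and without a clear precipitating event. Both open with the same order: "The PEEP should be increased to the maximum tolerated PEEP determined during the most recently performed SRM", held for 2 minutes.

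The maximum tolerated PEEP is defined in step (1) of the combined open lung procedure. If the staircase is completed, "the PEEP should be increased to the highest level of 40 cmH₂O. This should be determined as the maximum tolerated PEEP for this SRM". If it is abandoned, the level is one step lower than the step at which it stopped; the protocol's own example is "if marked desaturation occurs at 40 cmH₂O the maximum tolerated PEEP should then be determined as 30 cmH₂O".

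On whether the two manoeuvres are distinct, the list of contraindications refers to "both the staircase and the brief manoeuvre", and the independent version is introduced with: "A brief recruitment manoeuvre should be performed independently (ie. without an SRM and individual PEEP titration".

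**The concern.** A set-PEEP limit worded as absolute, with one named exception, stands in the same list as an order that exceeds it. After a staircase that was completed, or abandoned at 40, a clinician cannot obey both sentences.

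The practical risk is under-delivery. Someone who takes the cap at face value would hold the independent brief manoeuvre at 25 cmH₂O instead of 40 or 30. These manoeuvres have several triggers, including desaturation, circuit disconnection and return from a transfer. Under Management of severe hypoxaemia in the PHARLAP group, lack of improvement with a brief manoeuvre is one of the two routes to considering rescue therapy. Use of rescue therapy is a secondary outcome. If sites resolved the conflict differently, they would apply that step at different pressures.

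**Working it through.** No statistical figure is involved. The check sets the ordered PEEP beside the cap for each way a staircase can end.

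**Inputs**
- Cap: 25 cmH₂O, staircase excepted (brief recruitment manoeuvre instructions, last bullet).
- Independent brief manoeuvre: maximum tolerated PEEP for 2 minutes (same instructions, both versions).
- Staircase levels: a first step to 20 cmH₂O, then "In a stepwise fashion, this should be increased after 2 minutes to 30 cmH₂O (for 2 minutes) and then 40 cmH₂O (for 2 minutes" (combined open lung procedure, step 1).
- Maximum tolerated PEEP: 40 if completed; otherwise one level below the level at which it was abandoned (same step).
- Frequency limit: at most 4 brief manoeuvres in 24 hours, at least 2 hours apart.

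**Formula:** excess = maximum tolerated PEEP − 25.

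| Staircase outcome | Maximum tolerated PEEP | Excess over cap |
|---|---|---|
| Completed | 40 | 40 − 25 = 15 |
| Abandoned at 40 | 30 | 30 − 25 = 5 |
| Abandoned at 30 | 20 | 20 − 25 = −5, no conflict |
| Abandoned at 20 | PEEP before the staircase | conflict only if that already exceeded 25 |

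In the last row a conflict is implausible, because the first staircase step is an increase to 20. The conflict therefore arises in the default case, a staircase completed as planned, and in one of the abandoned cases.

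**Does the exception reach the independent manoeuvre?** It covers the staircase. The independent brief manoeuvre is defined as done without one, so no reading of the exception brings it in.

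**Time involved.** At the permitted maximum, 4 × 2 = 8 minutes in 24 hours would be spent above the cap. If the brief manoeuvre that ends the daily combined procedure counts towards the four, which the protocol does not say, the independent ones account for 3 × 2 = 6 minutes. Both are ceilings; the protocol gives no expected rate.

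**Does the cap make sense as a limit on maintained PEEP?** Yes. The bullets before it raise the daily optimal PEEP by 2.5 cmH₂O after an unexplained desaturation. From 22.5 this gives 22.5 + 2.5 = 25, which is allowed. From 25 it would give 25 + 2.5 = 27.5, which the cap holds to 25. Read this way, the sentence does useful work and cancels nothing.

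**The case against.** The strongest reply is that position in the text settles the meaning. The first bullet orders the rise to maximum tolerated PEEP, the second sets a new daily optimal PEEP, and the third, the cap, limits that new level. A third bullet cannot sensibly cancel the first bullet of the same procedure in the ordinary case. This stands as evidence of intent, and it is why severity is low. It does not remove the conflict: the sentence names an exception, which shows that its drafter had recruitment manoeuvres in mind, and the brief manoeuvre is not named.

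Three stronger readings are tempting, and the documents do not support them.

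1. *The brief manoeuvre inside the combined procedure breaches the cap too.* It is also ordered at the higher level, "using the PEEP level that was the maximum tolerated PEEP for the recently performed SRM". But the brief manoeuvre instructions themselves use SRM loosely for the whole combined procedure: they credit the SRM with setting the daily optimal PEEP, which is actually the job of the titration step. The section on severe hypoxaemia likewise treats the daily combined procedure as a form of staircase manoeuvre. On that usage the exception arguably covers the brief manoeuvre that ends the combined procedure. The total pressures there, 40 + 12 = 52 to 40 + 18 = 58 cmH₂O with inspiratory pressure 15 ± 3, should therefore not be presented as clear breaches. The figure of the combined procedure could not be checked.

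2. *Every brief manoeuvre becomes a reportable deviation.* The Protocol deviations section does mention any change to a described procedure, but it first defines a deviation as an unplanned departure from expected conduct. A brief manoeuvre at the ordered pressure is expected conduct. The Monitoring section says that the database will report violations, but describes no programmed check on PEEP above 25.

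3. *Patients would receive more pressure than intended.* The excesses of 15 and 5 describe the ordered manoeuvre, and the order is the same after the wording is corrected. They measure the conflict between two sentences and are not evidence of harm.

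**Conclusion.** The point holds for the independent brief recruitment manoeuvre. As written, the cap forbids what the neighbouring bullets order, by 15 cmH₂O after a completed staircase and by 5 cmH₂O after one abandoned at 40. There is no conflict after one abandoned at 30.

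This rests on the literal wording of the exception and on the definition of the independent manoeuvre as separate from a staircase. That the cap was meant for maintained PEEP is an inference from context, though a strong one. That some clinicians might apply it literally is a possibility; nothing in the documents shows that it happened.

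Severity is low. The intent can be recovered, the sample size does not depend on it, and the Statistical and analytical plan makes all analyses intention-to-treat, so the primary analysis stands. It deserves correction because it is a bedside pressure limit, and staff should not have to work out which of two instructions gives way.

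**What to change.** In the cap sentence, extend the exception to name the brief manoeuvre beside the staircase: *staircase and brief recruitment manoeuvres*. The clinical leads should first confirm that the cap was meant for maintained PEEP, and sites should then be told by memo.

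The cost is one phrase and one memo. No pressure value, procedure, patient number or analysis changes. The wording of the combined procedure needs no change: the cap already limits the PEEP set at the end of it, and the new exception would also remove any doubt about the brief manoeuvre inside it.
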